### 3.2.4. Health Economic Endpoints

Medical Resource Utilization and Health Economics related data including:

1. Hospitalization length of stay for index procedure and unscheduled re-hospitalizations
2. Healthcare resource utilization for index procedure, post procedure and rehospitalizations for unscheduled events

### 3.3. Rescue Therapy

In order to provide an evaluation of the device, rescue therapy should not be used prior to completion of the first three passes with the EMBOVAC™ Aspiration Catheter.

Rescue therapy is defined as:

- Any change in frontline device therapy to remove the target occlusion in a vessel at least 2mm in size.
- Use of intra cranial stenting during the procedure
- Use of an intra-arterial thrombolytic agent during the procedure (e.g., tissue plasminogen activator, urokinase, prourokinase)

Progression in therapy to address thrombus/occlusion that is no longer appropriate for treatment with EMBOVAC™ (e.g., use of another device to remove distal occlusion in a vessel smaller than 2mm) will be considered an appropriate evolution in the standard of care and NOT considered rescue therapy.

## 4. Study Population

### 4.1. Participant Inclusion Criteria

Investigators will assess potential subjects who are candidates for the study. Candidates who meet the protocol inclusion / exclusion criteria may be enrolled. The subject selection criteria are in place for protection of participants and to address factors that may compromise the outcome of the investigation or interpretation of the results.

Candidates for this study must meet ALL of the following criteria:

1. Subject  $\geq$  18 years old.
2. Subject experiencing acute ischemic stroke with angiographic confirmation of Large Vessel Occlusion (LVO) of the distal intracranial internal carotid artery, middle cerebral artery (M1 or M2) or anterior cerebral artery (A1 or A2).
3. A clinical decision has been made to use the EMBOVAC™ aspiration catheter prior to enrollment in the research.
4. EMBOVAC™ Aspiration Catheter is attempted to be used for the first 3 clot removal passes for the target intracranial occlusion (if 3 passes are needed) using A

Direct Aspiration First Pass Technique (ADAPT). Exception: it is not considered rescue therapy if use of another device is needed to remove distal occlusion in a vessel smaller than 2mm after the first pass.

5. Pre-stroke mRS  $\leq 1$
6. NIHSS  $\leq 30$
7. Informed consent has been provided by the subject or the subject's legally authorized representative.

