### **7. Study Schedule**

#### **7.1. Pre-Screening / Screening**

Subjects presenting with AIS to enrolling medical treatment facilities will be evaluated and treated by the physician according to the institutional practice prior to enrollment in the study. All assessment and imaging performed for this study are part of SOC for stroke treatment. Informed consent is mandatory and must be obtained before any data is captured in the eCRF.

A subject can be consented to participate in this study from the point of imaging confirming a large vessel occlusion up to 45 days post-procedure. During the eligibility screening, the investigator or designee will perform an initial evaluation of potential study subjects according to the inclusion/exclusion criteria. Post-procedure, the eligibility criterion to be confirmed will be the requirement for the EMBOVAC™ aspiration catheter and ADAPT to be attempted to be used in the first 3 passes, if required, unless evolution of care is required to remove a clot in a distal vessel of <2mm in diameter, and confirmation that all assessments were in alignment with the schedule of assessments (See Table 1 Schedule of Assessments).

For subjects in whom consent is sought, the investigator, or designee, will explain the research study to the subject and answer any questions that may arise. The possible risks and possible benefits of participation will be discussed. The subject will be asked to read, review and sign the EC approved informed consent form. The informed consent process is detailed further in Section 11.3.

All subjects screened will be documented on the Screening/Enrolment log, including the reason for non-participation for subjects who do not enroll.

If for any reason the subject does not meet the eligibility criteria when assessed by the investigator for inclusion in the study, the subject will not be considered enrolled in this study or be followed per this clinical protocol.

All subjects who provide informed consent will be entered into eCRF regardless of whether or not they participate in the study.

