### 10.4. Sample Size Justification

There is no statistical power calculation and no hypothesis tests for this post-market study. 100 subjects are deemed sufficient to characterize the performance of EMBOVAC™ Aspiration Catheter.

Approximately 100 subjects will be enrolled. With an enrolled sample size of 100 and an attrition rate of no more than 5%, the precision (margin of error) for the primary endpoint is anticipated to be around 8.0% based on 2-sided 95% confidence intervals, where the primary endpoint rate is estimated to be 80%.

$$\text{Margin of error} \approx 1.96 \times SE = 1.96 \times \sqrt{\frac{p(1-p)}{n}} = 1.96 \times \sqrt{\frac{0.8 \times (1-0.8)}{95}} = 8.0\%$$

where  $SE$  denotes the standard error and  $p$  denotes the proportion of subjects who achieve the primary endpoint.

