### **10.6. Measures to Minimize Bias**

Cerenovus will be diligent in controlling for bias by utilizing proper study design and implementation of the approved study protocol. EC approval will be obtained at all clinical sites prior to study initiation. Study agreements/contracts will be made with the hospitals/universities and all compensation for conduct of the study will be paid to the hospitals/universities and not to the investigators. Inclusion and exclusion criteria will be implemented to avoid selection bias.

An independent Clinical Events Committee (CEC) will review and adjudicate the safety endpoints, as specified in the CEC charter. CEC members will provide an impartial review and will not hold a financial interest in Cerenovus. An independent core laboratory will perform the angiographic assessments for the primary and secondary effectiveness

endpoints. These evaluations will be performed by an independent reader who does not hold a financial interest in Cerenovus.

Clinical outcomes will be measured in a standardized manner using the National Institutes of Health Stroke Scale, a standardized, objective, clinical assessment tool used to quantify and document the neurological status of patients and to act as a predictor for clinical outcomes. It is used to determine stroke and the severity of stroke.

Clinical outcomes will be measured in a standardized manner using the Modified Rankin Scale, a commonly utilized seven-point scale measuring functional outcome and disability in patients with stroke. The mRS measures independence and dependence related to activities of daily living and can be used over time to determine recovery or regression. In this study, 90 day mRS evaluations will be conducted by an independent evaluator who is not part of the interventional treating team, the patient's direct clinical care or involved in data entry (e.g., neurologist CRNC).

An independent CEC will review and adjudicate safety endpoints to determine whether they meet protocol-specified criteria. CEC members will provide an impartial and standardized review of these safety events.

An independent Imaging Core Lab will perform the angiographic assessments for the primary effectiveness endpoint, as well as the secondary effectiveness endpoints that are based on imaging. The Imaging Core Lab will provide an impartial and standardized review of imaging outcomes.

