Study monitors will have clinical research experience and be proficient at study monitoring. Study data will be source data verified (SDV) as specified in the monitoring plan using the subject's medical records, study source worksheets, clinic notes, and radiographic reports as applicable as source documentation.

In order to minimize potential bias, subject screening logs will be maintained at the sites. These will document all first-line aspiration mechanical thrombectomies performed at the site. All cases of EMBOVACTM being used in stroke treatment, will be taken into account for total screening numbers, noting why the potential subject was not enrolled.

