7.3	Demographic and Baseline Characteristics.....	7
7.4	Procedural Characteristics.....	7
7.5	Primary and Secondary Endpoints.....	7
7.5.1	Primary Endpoint.....	8
7.5.2	Secondary Endpoints	8
7.5.2.1	Secondary Effectiveness Endpoints.....	8
7.5.2.2	Secondary Safety Endpoints.....	9
7.6	Health Economic Endpoints.....	10
7.7	Clot Analysis	10
7.8	Analyses of Adverse Events (AEs).....	11
7.9	Plans for Interim Analyses	12
7.10	Handling of Missing Data	12
7.11	Sensitivity Analyses.....	12
7.12	Subgroup Analysis.....	12
7.13	Additional Analyses.....	13
7.14	Changes from Planned Analyses	13

1 Study Design

This is a prospective, multi-center, single-arm, post-market clinical follow-up study that will enroll approximately 100 subjects at approximately 10 sites primarily in Europe, with clot collection for follow-on histopathological analysis. Subjects will be included in the study for a period of 3 months after the procedure, including follow up visits at 24 hours, 7 days (or discharge) and 90 days after the procedure.

2 Treatment Assignment

This is a single arm study and all enrolled subjects are intended to be treated with the study device, the EMBOVAC Aspiration Catheter.

3 Interval Windows

Study reports will be summarized using analysis visits as defined below.

- 24 Hours post-procedure (-12 to +48 hours)
- 7-Day/Discharge (-1 to +7 days)
- 90-day follow-up (± 15 days)

The study schedule is to be adhered to as closely as possible for all subjects. Data will be summarized by scheduled visit. Measurements outside the analysis windows will be considered as missing in the analysis. In the case of repeated measurements taken at the same visit, the most recent measurement with non-missing values will be used unless specified otherwise.

4 Levels of Significance

No hypothesis tests are planned in the study. All confidence intervals will be reported at a two-sided 95% confidence level. These confidence intervals will not be used for statistical inferences, but for clinical reference purpose and are intended to convey precision in the estimates.

5 Analysis Sets

The following analysis sets are defined in the study:

- **Modified Intent-to-Treat (mITT) Analysis Set**

The mITT analysis set will consist of enrolled subjects who have received treatment (at least one pass; a pass being defined as use of aspiration followed by evaluation of revascularization with angiography) with the study device.

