7.2 Disposition of Study Subjects

The number and percentage of subjects in each analysis set will be provided, together with the summary of subjects who early terminated from the study with associated reasons.

Enrollment by site will be summarized for all consented subjects and each analysis set.

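### No rule requires that all or consecutive eligible EMBOVAC cases be approached for consent, the site may by then know the angiographic result, and no planned analysis reports the screening log

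*Protocol*

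**What the plan says.** **Timing.** The primary endpoint is the Core Lab's final mTICI at the end of the procedure (Protocol 3.2.1). The site records its own mTICI for each pass (7.3). Inclusion criterion 4, on the first three passes, is confirmed after the procedure, as is agreement of the assessments with the schedule (7.1). A subject counts as enrolled only when all criteria are confirmed and consent is given (7.3). Consent may be sought at any time from imaging confirmation of the occlusion to day 45 (7.1, 11.3.1).

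**Choice of patients.** Protocol 4.1: "Candidates who meet the protocol inclusion / exclusion criteria may be enrolled". Protocol 7.1: "For subjects in whom consent is sought, the investigator, or designee, will explain the research study to the subject". Neither document says that consent must be sought from all, or from consecutive, eligible patients.

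**Safeguards.** Protocol 10.6: "Inclusion and exclusion criteria will be implemented to avoid selection bias". The same section requires a site log of all first-line aspiration thrombectomies, with every case of EMBOVAC "being used in stroke treatment, will be taken into account for total screening numbers, noting why the potential subject was not enrolled".

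**Analysis.** Disposition in Protocol 10.5.2 covers enrolled subjects. SAP 7.2: "Enrollment by site will be summarized for all consented subjects and each analysis set". The sensitivity analyses in SAP 7.11 concern the 90-day mRS only. No planned output uses the log.

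**The concern.** This is a single-arm study without a hypothesis test, so the success rate and its interval are the whole primary result. They are offered as real-world performance, which is a fair reading only if the chance of being enrolled does not depend on the result.

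The stated safeguards do not reach this point:

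- Eligibility criteria cannot control a choice made among patients who meet them.
- Blinded Core Lab reading (Protocol 6.1.2) protects the score, not the selection of patients to be scored.
- Protocol 11.3.1 says that the 45-day window prevents bias, but its reasons concern the patient's capacity and access to relatives, not the angiographic result.

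The protocol introduces the log as a measure against bias, yet its counts stop at the site.

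**Working it through.** **1. Inputs**

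- Assumed true rate p = 0.80. Protocol 10.4: "where the primary endpoint rate is estimated to be 80" per cent.
- Analysed n = 95, from 100 enrolled and 5% attrition (Protocol 10.4).
- Two-sided 95% interval by normal approximation (SAP 4 and 7.5.1).
- r = enrolment probability of an angiographic failure divided by that of a success. **This is an assumption. The documents give no value.**

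**2. The plan's own figure**

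1.96 × √(0.8 × 0.2 / 95) = 0.0804, or 8.0 points. It reproduces. It measures sampling error only.

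**3. Expected rate under selection**

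Expected rate = p / (p + (1 − p) × r). With p = 0.80:

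| r | Calculation | Expected rate | Shift (points) | Coverage of true 80% by the 95% interval, n = 95 |
|---|---|---|---|---|
| 1.0 | 0.8 / 1.00 | 80.0% | 0 | 94.0% |
| 0.9 | 0.8 / 0.98 | 81.6% | +1.6 | 90.4% |
| 0.75 | 0.8 / 0.95 | 84.2% | +4.2 | 75.3% |
| 0.5 | 0.8 / 0.90 | 88.9% | +8.9 | 25.5% |

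Coverage is the exact binomial probability, at the shifted rate, that the normal-approximation interval contains 0.80.

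The shift equals the stated margin when r = (0.8 / 0.8804 − 0.8) / 0.2 = 0.54.

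**4. Why these are upper values**

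The table treats the site as selecting on the primary endpoint itself. In fact the site knows only its own reading. Suppose, again as an assumption, that sites call 60% to 90% of Core Lab failures failures, and 3% of Core Lab successes failures. With r = 0.75 applied to the site reading:

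- Relative enrolment of Core Lab successes: 0.97 + 0.03 × 0.75 = 0.9925.
- Relative enrolment of Core Lab failures: 0.10 + 0.90 × 0.75 = 0.775 (90% recognised), or 0.40 + 0.60 × 0.75 = 0.85 (60% recognised).
- Effective r: 0.775 / 0.9925 = 0.781, or 0.85 / 0.9925 = 0.856.
- Expected rate: 0.8 / (0.8 + 0.2 × 0.781) = 83.7%, or 0.8 / (0.8 + 0.2 × 0.856) = 82.4%, instead of 84.2%.

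**5. What the log counts could show**

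Take 76 successes in 95 analysed (80%) and an assumed 20 cases that were eligible apart from consent but not enrolled. The rate among all 115 lies between 76/115 = 66.1% (all 20 failures) and 96/115 = 83.5% (all 20 successes). With 5 such cases the range is 76/100 = 76.0% to 81/100 = 81.0%. The number of unenrolled cases therefore largely decides how far the primary rate can be trusted as a rate for all eligible cases.

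**The case against.** A reader might infer that investigators always decide after seeing the angiogram, that the primary rate is inflated, or that selection would go wholly undetected. The documents support none of these.

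- **Timing.** Consent may be sought as soon as the occlusion is confirmed, so a patient or representative can be approached before any pass. Only formal enrolment must wait. The documents give no split of consent before and after the procedure, so the most they support is that the investigator may decide knowing the result.
- **Consent instruction.** Protocol 11.3.1 asks for all reasonable efforts to obtain consent from a representative when the subject cannot give it, including after death or in severe cases. This works against losing poor outcomes. It does not cover a capable patient with a poor angiogram.
- **The word may.** It is natural in 4.1, because consent is itself inclusion criterion 7. The gap is the missing approach rule, not the verb alone.
- **Detectability.** The log is a retained site document (13.1.8), and monitoring may include checking study logs (Section 9). Everyone who consents enters the eCRF (7.1). What is missing is a reported analysis, not the record.
- **Size.** Every value of r is assumed. At r = 0.9 the shift is 1.6 points, well inside the margin.
- **Site cap.** Protocol 4.3 limits each site to 20% of enrolment, about 20 subjects, so an unqualified rule to enrol every case would contradict it.

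These points limit the claim and shape the remedy. They do not supply an approach rule or a planned use of the log.

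**Conclusion.** The point holds as a cheap improvement. The plan as written permits selection on a known angiographic result among eligible patients, and no planned output would show it.

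The bias is possible, not demonstrated, and the documents do not allow its size to be derived. At a true rate of 80%, the assumed ratios of 0.9, 0.75 and 0.5 shift the expected rate by 1.6, 4.2 and 8.9 points against a stated margin of 8.0. All three are upper values if site and Core Lab readings differ as illustrated. The margin in Protocol 10.4 is arithmetically correct, but it does not cover this source of error.

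**What to change.** **Protocol 4.1 and 7.1.** Require that consent be sought for every consecutive EMBOVAC case that meets all criteria other than consent, whatever the angiographic or clinical result, until the site reaches its enrolment cap (4.3). Record on the log whether the case was approached, and the reason for non-enrolment.

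**SAP 7.2.** Add a flow table by site from aggregate log counts: EMBOVAC cases, eligible apart from consent, approached, consented, analysed. Counts alone respect the rule that no eCRF data are captured before consent.

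**Optional.** Beside the primary rate, show bounds that count all cases eligible apart from consent but not enrolled, whether not approached or not consenting, first as failures and then as successes. Leave out cases that arose after a site reached its cap.

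**Cost.** Sites must approach all such cases, the log gains one field (no passage says that it records approach), and the protocol change needs ethics committee approval (11.2). The SAP table alone can be added before database lock. Without the new field its approached column can be filled only where the logged reasons allow. The table shows how much room there was for selection. It does not prove that selection took place.

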#### 4.2. Exclusion Criteria

Candidates will be excluded from participation if ANY of the following apply:

1. Potential study candidate has already undergone standard of care assessments or treatment that deviate from the clinical research protocol requirements (e.g., 24 hour imaging conducted outside the protocol specified window).
2. All patients with severe hypertension on presentation (SBP  $> 220$  mmHg and/or DBP  $> 120$  mm Hg). All patients, in whom intravenous therapy with blood pressure medications is indicated, with hypertension that remains severe and sustained despite intravenous antihypertensive therapy (SBP  $> 185$  mmHg and/ or DBP  $> 110$  mmHg).
3. Known cerebral vasculitis.
4. Known cancer with life expectancy less than 12 months.
5. Stenosis, or any occlusion, in a vessel proximal to the target occlusion that requires treatment or prevents access to the site of occlusion.
6. Computed tomography (CT) or Magnetic Resonance Imaging (MRI) evidence of recent/ fresh hemorrhage on presentation.
7. Baseline computed tomography (CT) or MRI showing mass effect or intracranial tumor (except small meningioma).
8. Evidence of dissection in the extra or intracranial cerebral arteries.
9. Occlusions in multiple vessels
10. Confirmation of positive pregnancy test according to site specific standard of care (e.g. test, verbal communication).
11. Currently participating in an investigational (drug, device, etc.) clinical trial that may confound study endpoints. Patients in observational, natural history, and/or epidemiological studies not involving intervention are eligible.

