## SCHEDULE OF ASSESSMENTS

**Table 1 Schedule of Assessments**

Assessments	Enrollment				Follow-up	
	Baseline	Procedure	24hrs post-procedure (+/- 12 hrs)	7 days/ discharge (- 1/+7 days) (whichever comes first)	📞 90 Day Follow-up (+/- 14 days)	Unscheduled (6)
Eligibility Screening	X	X	X	X		
Informed Consent	Patient consent may be obtained up to 45 days post procedure					
Demographics and Medical History	X					
IV t-PA administration	O					
Imaging 	X		X			O
NIH Stroke Scale (NIHSS)	X 		X 	O	O	O
Modified Rankin Scale (mRS)	X 			O	X 	O
Angiography 		X				
Review of Reportable AEs 		X	X	X	X	X
Clot Collection 		X				
Health Economics Data Collection		X	X	X	X	X

(1) Imaging will be sent to independent Imaging Core Lab for review

(2) Procedural angiography will be sent to Imaging Core Lab for review

(3) Per pass clot collection to be sent to Clot Analysis Lab for processing

(4) If more than one NIHSS was performed during this time period, select the worst (highest) value

(5) To be administered pre-procedure by a qualified evaluator; pre-stroke mRS should reflect the subject's condition just prior to the stroke onset. For example, if the subject was hospitalized during stroke onset, the subject's reason for hospitalization should be taken into account when evaluating the subject's pre-stroke mRS

(6) Assessments should be completed for unscheduled visits from the time of Discharge up to (but not including) the 90-day Follow-up, where imaging, NIHSS or mRS is performed as part of stroke management care for the subject

(7) The 90 day mRS must be performed by a qualified independent evaluator. This may be performed by phone per the site's SOC.

(8) AEs will be reported and recorded (via eCRF) if any of the following apply: (a) The event is neurological in nature (b) The event is a serious adverse event (SAE) (c) AE where causality is related to the device or procedure.

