### **11.3. Informed Consent and Data Release Form Process**

#### **11.3.1. Consent and Other Informational Documents Provided to Participants**

Subject's informed consent must be obtained and documented according to the principles of informed consent. Due to the emergent nature of AIS, consent may be obtained up to 45 days post-procedure, as permitted by the local regulations and EC.

The 45-day window of consent is a mid-point in the patient's follow-up and will prevent study bias for the following reasons:

- Due to the nature of AIS and its treatment, subjects may require several weeks to regain the capacity to provide their consent to be part of the study or to physically sign the informed consent form
- Due to precautionary restrictions at hospitals to prevent the spread of infectious disease, it is not always possible for the treating physician to request the subject's LAR/relative to provide informed consent on the subject's behalf. The 45 day consenting window gives the physicians more chances to connect with subject's relatives

In the event that a subject is not capable of giving their informed consent, all reasonable efforts will be made to obtain informed consent from the subject's LAR (for example, relative or caregiver). This includes cases where the subject dies during the intervention or shortly thereafter, before they can provide their informed consent, or when the severity of the subject's condition prohibits them from providing informed consent. This will vary from case to case, depending on the status / mental state of the patient or if the patient is in life threatening condition at the time of screening. In this case, the investigators should follow their standard practice to determine if a patient is able to provide their own consent or whether consent should be obtained from a patient's LAR.

The EC must review and approve an informed consent form (ICF) specific to this study. Cerenovus will provide each study center with an example ICF or data release form. The clinical center, to meet specific EC requirements, may modify this example ICF. The original, subject's ICF must be retained by the investigational site for monitoring, and a copy provided to the subject.

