## 14. Protocol Deviations

The investigator is responsible for ensuring that the clinical investigation is conducted in accordance with the procedures described in the protocol, and any conditions required by the reviewing EC. A protocol deviation is a failure to comply (intentionally or unintentionally) with the requirements of the clinical study as specified in the protocol. Examples of protocol deviations include late visits, missed visits, required follow-up testing not completed, visit out of window, non-adherence to inclusion/exclusion criteria, etc. and shall be reported to the Sponsor through the eCRFs.

Any standard of care assessments performed outside of the protocol requirements prior to consent/enrollment will be considered an eligibility deviation. Deviations will be reviewed and assessed by the Sponsor.

It is the responsibility of the site to use vigilance to identify and report deviations to the Sponsor and EC per guidelines. The study monitors shall verify that the conduct of the study is in compliance with the approved protocol and applicable regulations and shall identify deviations and any issues of noncompliance. Corrective and preventative actions will be implemented promptly as necessary and significant protocol deviations that raise subject safety concerns or indicate repeat noncompliance may be grounds for investigator disqualification.

The investigator is not allowed to deviate from the protocol except under emergency circumstances to protect the rights, safety and well-being of study participants. Under emergency circumstances, deviations from the protocol to protect the rights, safety and well-being of human subjects may proceed without prior approval of the sponsor and the ethics committee. Such deviations shall be documented and reported to the sponsor and ethics committee as soon as possible.

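### Enrolment can depend on whether 24-hour imaging and NIHSS were done on schedule, so patients not yet enrolled by then can be selected on their post-treatment course

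*Protocol*

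**What the plan says.** Exclusion criterion 1 (Protocol 4.2, repeated in the Protocol Summary) removes a candidate whose standard-of-care record already shows "assessments or treatment that deviate from the clinical research protocol requirements (e.g., 24 hour imaging conducted outside the protocol specified window". Protocol 7.1 goes further. Among the items to establish after the procedure it lists "confirmation that all assessments were in alignment with the schedule of assessments". Table 1 requires both imaging and NIHSS at the visit headed "24hrs post-procedure (+/- 12 hrs)", and marks eligibility screening at baseline, procedure, 24 hours and 7 days/discharge.

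Consent may be obtained "from the point of imaging confirming a large vessel occlusion up to 45 days post-procedure" (Protocol 7.1). If eligibility is not met, "the subject will not be considered enrolled in this study or be followed per this clinical protocol". Protocol 10.2 and SAP section 5 build both the mITT and the safety set from enrolled subjects.

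Two other sections bear on the same patients. On seeking consent from a representative, Protocol 11.3.1 states: "This includes cases where the subject dies during the intervention or shortly thereafter, before they can provide their informed consent". Protocol 14 states: "Any standard of care assessments performed outside of the protocol requirements prior to consent/enrollment will be considered an eligibility deviation", and adds that the Sponsor reviews and assesses deviations.

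**The concern.** The 24-hour scan and NIHSS are outcome data: they feed the sICH and 24-hour NIHSS safety endpoints (Protocol 3.2.3 and 7.4). Once their timing becomes an entry test, a patient who has already been treated can be kept out of the study because of what happened after treatment. That patient then leaves every denominator.

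Whether a scan and an NIHSS fall in the window is unlikely to be independent of clinical course. A patient who dies within hours has neither. A patient who deteriorates may be imaged early and not again in time. A stable patient is more likely to follow the routine. If that pattern holds, sICH, early neurological worsening and mortality would be understated and mRS 0-2 overstated. The study is meant to describe real-world performance, and its interim results are intended for regulatory submissions (Protocol 10.5.7).

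The rule also depends on the consent date. An off-schedule scan is an ordinary deviation in a patient already enrolled, but a possible bar to entry in one approached later.

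**Working it through.** **1. The plan's own figure.** The only computed quantity is the margin of error for the primary endpoint: 1.96 × √(0.8 × 0.2 / 95) = 0.0804, which agrees with the stated 8.0%. It describes sampling precision and is not affected by this point. The documents give no expected safety rate and no expected share of refusals.

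**2. The rules applied to particular patients.** The protocol window is 24 − 12 = 12 h to 24 + 12 = 36 h. The SAP window (section 3) is 24 − 12 = 12 h to 24 + 48 = 72 h.

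| Patient not yet enrolled at the 24-hour visit | Criterion 1 | Protocol 7.1, read literally | Other text |
|---|---|---|---|
| Scan and NIHSS at 24 h | passes | passes | none |
| Dies before 12 h | not clearly reached: nothing off-window was done | can be refused: no in-window assessment exists | 11.3.1 expects consent through a representative |
| Scanned early for deterioration, scanned again in window | passes | passes | 6.1.1 treats deterioration imaging as additional |
| Scanned early, no further in-window scan | arguable | can be refused | 14: eligibility deviation |
| Routine scan between 36 h and 72 h | excluded | can be refused | within the SAP window, so valid for analysis |

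A patient enrolled before the visit is not exposed to the rule. For that patient Protocol 14 treats late, missed or out-of-window visits as ordinary deviations.

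**3. Illustration of size (all inputs assumed).** Let p be the true event rate among treated patients, fe the share of event patients refused, and fn the share of event-free patients refused. Then

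observed rate = p(1 − fe) / [p(1 − fe) + (1 − p)(1 − fn)].

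| fe | fn | Mortality, true 15% | sICH, true 5% |
|---|---|---|---|
| 10% | 0 | 13.7% | 4.5% |
| 20% | 0 | 12.4% | 4.0% |
| 30% | 0 | 11.0% | 3.6% |
| 50% | 0 | 8.1% | 2.6% |
| 30% | 10% | 12.1% | 3.9% |
| 10% | 10% | 15.0% | 5.0% |
| 5% | 15% | 16.5% | 5.6% |

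For example, with fe = 30% and fn = 10%: 0.15 × 0.7 / (0.15 × 0.7 + 0.85 × 0.9) = 0.105 / 0.870 = 12.1%. The last two rows show that equal refusal shares give no bias and that a larger share among event-free patients reverses the sign.

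**4. The same in counts.** If 5 sICH are seen in 100 enrolled subjects (5.0%, exact 95% CI 1.6% to 11.3%) and 2 further sICH patients were refused, the rate is 7/102 = 6.9% (2.8% to 13.6%). If 15 deaths are seen in 100 (15.0%, 8.6% to 23.5%) and 2 further deaths were refused, it is 17/102 = 16.7% (10.0% to 25.3%).

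**The case against.** The other side has a good deal on its side.

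- **Direction.** A reader might infer that the safety rates are biased low. That requires event patients to be refused more often than event-free patients, and the documents give neither share. The rule also removes late routine scans, and patients who deteriorate may be imaged more rather than less.
- **Early deaths.** A reader might infer that early deaths are barred outright. Criterion 1 concerns assessments already carried out, and an absent scan is not an out-of-window scan, so this route rests on Protocol 7.1 alone. That check could be read as covering only assessments that fell due while the patient was alive. Protocol 11.3.1 plainly intends some early deaths to be enrolled, and the mRS analysis scores deaths as 6.
- **Bar or deviation.** Protocol 14 lists breaches of the entry criteria among reportable deviations and sends deviations to the Sponsor for review, so refusal may not be automatic.
- **Scope and size.** Only patients not enrolled by 24 hours are exposed, and their share is unknown. The study is descriptive, and the shifts in step 4 lie within the confidence intervals of the observed rates.
- **Screening log.** Sites record why EMBOVAC cases were not enrolled (Protocol 7.1 and 10.6), so refusals can be counted.

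All of this limits the claim without removing it. Ambiguity about who may be refused leaves the denominator to each site's reading. Representative consent meets the consent requirement but not the assessment check. The log need not carry outcomes, and the SAP plans no analysis of refused patients. A shift inside a confidence interval is still a shift that the interval does not account for.

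**Conclusion.** The point stands in this form: for patients not yet enrolled at the 24-hour visit, the protocol lets entry to both analysis sets depend on the timing or existence of post-treatment endpoint assessments, and later analysis cannot restore those refused. Favourable distortion of sICH, 24-hour NIHSS, 90-day mortality and mRS 0-2 is the expected result, on condition that event patients are refused more often. It is not demonstrated. The percentages above are illustrations on assumed rates, not estimates for this trial.

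Three internal conflicts need no assumption. Protocol 7.1, read literally, permits refusal of early deaths that 11.3.1 intends to include. Protocol 4.2 and 7.1 make an off-schedule assessment a reason not to enrol, while 14 makes it a deviation for review. A scan between 36 h and 72 h can bar enrolment under the protocol although the SAP would accept it.

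**What to change.** 1. Limit criterion 1 and the Protocol 7.1 post-procedure check to baseline and index-procedure information. Delete the example "24 hour imaging conducted outside the protocol specified window" in 4.2 and the Protocol Summary, and delete the test "confirmation that all assessments were in alignment with the schedule of assessments" in 7.1.
2. Treat an early, late or absent post-procedure assessment as a protocol deviation or a missing value in an enrolled subject, whatever the consent date. SAP section 3 already sets measurements outside its windows to missing.
3. Reconcile Protocol 4.2, 7.1, 11.3.1 and 14, so that the same event has the same consequence throughout and the position of early deaths is explicit.
4. For patients already screened, tabulate from the existing log how many treated patients were refused for this reason, and print that number beside sICH and mortality.

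The cost is a protocol amendment, which needs ethics committee approval before it takes effect (Protocol 11.2), and one added SAP table. The study will carry some out-of-window or missing 24-hour values, and the safety rates may be less favourable. The log count shows how many patients are concerned but not their outcomes, so it bounds the problem for those already refused without correcting it.
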